7.2 Cabozantinib

7.2.1 Product Description and Administration

Exelixis (one of the two co-sponsors) will provide adequate supplies of Cabozantinib, which will be supplied as 40-mg yellow film-coated tablets and also as 20-mg yellow film-coated tablets.

The components of the tablets are listed below.

40 mg Cabozantinib tablets are yellow film-coated, oval shaped with no score, and debossed with "XL" on one side and "60" on the other side.

20 mg CABOMETYX tablets are yellow film-coated, round with no score, and debossed with "XL" on one side and "20" on the other side.

Table 3. Cabozantinib Tablet Components and Composition

Ingredient	Function	% w/w ^a
Cabozantinib Drug Substance (25% drug load as free base)	Active Ingredient	31.68
Microcrystalline Cellulose (Avicel® PH-102)	Filler	38.85
Lactose Anhydrous (60M)	Filler	19.42
Hydroxypropyl Cellulose (EXF)	Binder	3.00
Croscarmellose Sodium (Ac-Di-Sol®)	Disintegrant	6.00
Colloidal Silicon Dioxide	Glidant	0.30
Magnesium Stearate	Lubricant	0.75
Opadry® yellow film coating which includes HPMC 2910/hypromellose 6 cp, titanium dioxide, triacetin, and iron oxide yellow	Film Coating	4.00

^a weight fraction, expressed in percentage; HPMC, Hydroxypropyl methylcellulose

Preparation, Storage and Stability

Store at 20°C to 25°C (68°F to 77°F); excursions permitted from 15°C to 30°C (59°F to 86°F).

Administration

Refer to the treatment section for specific administration instructions. Oral: 40 mg once daily, continue as long as benefiting clinically or until unacceptable toxicity (Choueiri 2021); do not exceed 60 mg daily. Administer on an empty stomach (1 hour before or 2 hours after eating).

Note: The prescribing information (for Cometriq) describes when to give food with respect to Cabozantinib; no food should be consumed for at least 2 hours before or for at least 1 hour after the Cabozantinib dose. Swallow whole; do not crush tablets. Do not substitute Cabozantinib tablets.

7.2.2 Adverse Events from Cabozantinib monotherapy

Consult the package insert and investigator brochure for the most current and complete information.

The **most frequent AEs experienced** by $\geq 20\%$ of subjects treated with Cabozantinib in descending order of frequency were diarrhea, fatigue, nausea, decreased appetite, vomiting, weight decreased, PPE, constipation, hypertension, dysgeusia, dysphonia, and asthenia. For a full description of the safety profile of Cabozantinib, refer to the Cabozantinib Investigator's Brochure.

Other **medically important** but less frequent AEs including arterial thrombotic AEs (e.g., TIA, and MI) and venous thrombotic AEs (e.g., DVT and PE), severe hemorrhagic events, proteinuria, wound-healing complications, GI perforation, abscesses including intra-abdominal and pelvic abscess, GI and non-GI fistula formation, osteonecrosis, and Reversible Posterior Leukoencephalopathy Syndrome (RPLS).

Adverse events associated with **laboratory abnormalities** experienced by $\geq 5\%$ of subjects treated with Cabozantinib in descending order of frequency were anemia, AST increased, ALT increased,

hypothyroidism, hypokalemia, hypomagnesemia, thrombocytopenia, hypocalcemia, hypophosphatemia, lactate dehydrogenase (LDH) increased, lipase increased, neutropenia, hyponatremia, ALP increased, leukopenia, and hyperglycemia.

Adverse events may occur within the first few weeks in the course of treatment with Cabozantinib, as Cabozantinib is expected to reach steady state exposure at approximately 2 weeks following first dose. Events that generally have an **early onset** include hypocalcemia, hypokalemia, thrombocytopenia, hypertension, PPE, abdominal pain, mucosal inflammation, constipation, diarrhea, and vomiting. Adverse events should be managed with supportive care at the earliest signs of toxicity. Dose reductions and treatment interruptions should be considered. Dose reductions are recommended for events that, if persistent, could become serious or intolerable.

Cabozantinib should be discontinued for the following AEs:

visceral perforation or fistula formation, severe hemorrhage, serious arterial thromboembolic events, nephrotic syndrome, hypertensive emergency, persistent uncontrolled hypertension despite optimal medical management, and RPLS.

Gastrointestinal Disorders

Gastrointestinal perforation, GI fistula, and intra-abdominal and pelvic abscess: After starting treatment with Cabozantinib, subjects should be monitored for early signs of GI perforation such as abdominal pain, nausea, emesis, constipation, and fever especially if known risk factors for developing GI perforation or fistula (Turnage et al, 2016) are present. Discontinue Cabozantinib and initiate appropriate management in subjects who have been diagnosed with GI perforation or fistula.

Diarrhea: Subjects should be instructed to notify their physician immediately at the first signs of poorly formed or loose stool or an increased frequency of bowel movements. Guidelines for the evaluation and management of diarrhea are shown in Appendix D. Administration of antidiarrheal/antimotility agents is recommended at the first sign of diarrhea as initial management. Some subjects may require concomitant treatment with more than one antidiarrheal agent. When therapy with antidiarrheal agents does not control the diarrhea to tolerable levels, Cabozantinib should be temporarily interrupted or dose reduced. When the diarrhea is controlled, retreatment with Cabozantinib may be acceptable per investigator decision. In addition, general supportive measures should be implemented such as continuous oral isotonic hydration, correction of fluid and electrolyte abnormalities, small frequent meals, and stopping lactose-containing products, high-fat meals, and alcohol.

Recurrent or prolonged diarrhea can be associated with anal or perianal skin erosions which increase the risk for anal abscesses, fistulas, or proctitis. Good personal hygiene should be emphasized. Regular examinations of the perianal region should be performed whenever diarrhea has occurred during treatment with Cabozantinib. Infections of the perianal region should be treated per local guidelines.

Nausea and vomiting: Antiemetic agents are recommended as clinically appropriate for treatment or prophylaxis of nausea and vomiting, along with supportive care. Dehydration and electrolyte abnormalities may be associated with vomiting and monitoring for and correction of fluid and electrolyte disturbances should be implemented. Antiemetic medications should be assessed for potential drug interactions.

Non-gastrointestinal Fistula

Complications from radiation therapy especially of the thoracic cavity including mediastinum have been identified as a possible predisposing risk factor for non-GI fistula formation in subjects undergoing treatment with VEGF pathway inhibitors.

Discontinue Cabozantinib and initiate appropriate management in subjects who have been diagnosed with a non-GI fistula.

Hemorrhage

Hemorrhagic events, including serious and sometimes fatal events, have been reported with Cabozantinib. Subjects should be monitored for bleeding events with serial complete blood counts and physical examination while on study. The risk of hemorrhage in Cabozantinib-treated subjects with brain metastases has not been thoroughly analyzed. Subjects enrolled with treated and stable brain metastases should be monitored with a high index of suspicion if symptoms that could be due to a CNS hemorrhage occur.

Cabozantinib should be discontinued in subjects with serious and life-threatening bleeding events or recent hemoptysis (≥ 2.5 mL of red blood).

Thromboembolic events

Thromboembolic events are frequent in cancer subjects due to procoagulant changes induced by the malignancy or anticancer therapy. DVT and PE have been observed in clinical studies with Cabozantinib, including fatal events. Subjects who develop a PE and/or DVT should have study treatment interrupted until therapeutic anticoagulation is established. Treatment with Cabozantinib may be resumed in subjects with PE or DVT if it is determined that the event is uncomplicated and that the subject is deriving clinical benefit from Cabozantinib treatment and that anticoagulation does not place them at a significant risk that outweighs the benefit of resuming treatment per discretion of the investigator and according to individual protocols. Low molecular weight heparins are the preferred management for thrombotic events; oral anticoagulants (e.g., warfarin or other coumarin-related agents, direct thrombin or direct FXa inhibitors, or antiplatelet agents, or chronic use of aspirin above low dose levels for cardioprotection per local applicable guidelines) are not allowed except under the following circumstances:

Allowed anticoagulants are the following:

- a. Prophylactic use of low-dose aspirin for cardio-protection (per local applicable guidelines) and low-dose low molecular weight heparins (LMWH).
- b. Therapeutic doses of LMWH or anticoagulation with direct factor Xa inhibitors rivaroxaban, edoxaban, or apixaban in subjects without known brain metastases who are on a stable dose of the anticoagulant for at least 1 week before first dose of study treatment without clinically significant hemorrhagic complications from the anticoagulation regimen or the tumor.

Arterial thrombotic events (e.g., TIA, MI) have been observed in studies with Cabozantinib. Further treatment with Cabozantinib should be discontinued in subjects who develop an acute MI, cerebral infarction, or any other clinically significant arterial thromboembolic complication.

Hypertension

Appendix D provides treatment guidelines for hypertension deemed related to Cabozantinib. Blood pressure should be monitored in a constant position visit to visit, either sitting or supine in

a relaxed setting. Decisions to reduce or interrupt the dose of study treatment must be based on BP readings taken by a medical professional and must be confirmed with a second measurement at least 5 minutes following the first measurement. Cabozantinib should be discontinued in subjects with hypertensive emergency.

Stomatitis and Mucositis

Preventive measures may include a comprehensive oral examination to identify and treat any potential risk for complications before study treatment is initiated. Appropriate correction of local factors should be instituted as indicated, such as modification of ill-fitting dentures and appropriate care of gingivitis. During treatment with Cabozantinib, good oral hygiene and standard local treatments such as non-traumatic and non-irritating cleansing, and oral rinses (e.g., with a weak solution of salt and baking soda) should be maintained. Lips should be kept moisturized with lip balm. The use of lipstick, lip-gloss, and Vaseline should be avoided.

Local treatment should be instituted at the earliest onset of symptoms. Obtain bacterial/viral culture if oral infection is suspected and treat infection as clinically indicated.

Skin and Subcutaneous Tissue Disorders

Wound healing and surgery:

Cabozantinib has the potential to cause wound healing complications and wound dehiscence which may even occur long after a wound has been considered healed. Therefore, surgical and traumatic wounds must not only be completely healed prior to starting cabozantinib treatment but must also be monitored for wound dehiscence, wound infection and other signs of impaired wound healing while the subject is being treated with cabozantinib. If dehiscence occurs, cabozantinib treatment should not be restarted until complete healing has taken place.

Treatment with cabozantinib should be stopped at least 3 weeks prior to elective surgery. Do not administer cabozantinib for at least 2 weeks after major surgery and until complete wound healing.

Palmar-plantar erythrodysesthesia (PPE; also known as hand-foot syndrome), skin rash (including blister, erythematous rash, macular rash, skin exfoliation, dermatitis acneiform, and papular rash), pruritus, dry skin, erythema, pigmentary changes, and alopecia have been reported with Cabozantinib. All subjects on study should be advised on prophylactic measures including the use of emollients, removal of calluses, avoidance of exposure of hands and feet to hot water leading to vasodilatation, protection of pressure-sensitive areas of hands and feet, and use of cotton gloves and socks to prevent injury and keep the palms and soles dry.

Early manifestations include tingling, numbness, mild hyperkeratosis, and symmetrical red and swollen areas on the palms and soles. The lateral sides of the fingers or periungual zones may also be affected. Adequate interventions are required to prevent worsening of skin symptoms such as blisters, desquamations, ulcerations, or necrosis of affected areas. Analgesics may be required for pain control.

Aggressive management of symptoms is recommended, including early dermatology referral.

Osteonecrosis

Osteonecrosis has been reported in subjects treated with Cabozantinib. Additional risk factors include use of bisphosphonates and denosumab, chemotherapy and anti-angiogenic drugs, use of corticosteroids, local radiotherapy, and dental or orofacial surgery procedures.

Osteonecrosis of the jaw (ONJ) can manifest as jaw pain, osteomyelitis, osteitis, bone erosion, tooth or periodontal infection, toothache, gingival ulceration, or gingival erosion. Persistent pain

or slow healing of the mouth or jaw after dental surgery may also be manifestations of osteonecrosis.

Advise subjects regarding oral hygiene practice and to quickly report symptoms to investigator. Perform an oral examination prior to initiation of cabozantinib and periodically during cabozantinib treatment. Caution should be used in subjects receiving bisphosphonates and/or denosumab.

Invasive dental procedures should be avoided. In cases where dental procedures are unavoidable, treatment with Cabozantinib should be interrupted for at least 4 weeks prior to the procedure and resumed after complete wound healing has occurred. Bone healing may often require a protracted time. Withhold cabozantinib for development of ONJ until complete resolution.

Proteinuria

Proteinuria has been reported with Cabozantinib. Proteinuria should be monitored by measuring UPCR Appendix D provides treatment guidelines for proteinuria deemed related to Cabozantinib.

Cabozantinib should be discontinued in subjects who develop nephrotic syndrome (proteinuria > 3.5 grams per day in combination with low blood protein levels, high cholesterol levels, high triglyceride levels, and edema).

Nervous System Disorders

Cabozantinib appears to represent minimal risk of adverse neurological effects based on nonclinical Good Laboratory Practice (GLP)-compliant toxicology studies. Dysphonia, dysgeusia, headache, dizziness, confusional state, convulsion, depression, memory impairment, hypoesthesia, peripheral neuropathy, insomnia, ataxia, and encephalopathy have been observed in clinical studies with Cabozantinib. The development of any new or progressive, unexplained neurological symptoms should be assessed for underlying causes.

Reversible Posterior Leukoencephalopathy Syndrome (RPLS) has been reported. RPLS should be considered in any subject presenting with seizures, headache, visual disturbances, confusion or altered mental function. Cabozantinib treatment should be discontinued in subjects with RPLS.

Blood and Lymphatic System Disorders

Hematological toxicities (i.e., neutropenia and thrombocytopenia) and associated complications have been observed after administration of Cabozantinib and may be managed with dose interruptions and/or dose reductions. Subjects with hematologic toxicities may require additional or more frequent laboratory tests according to institutional guidelines.

Dose reductions or dose interruptions for hematological toxicities are not mandated but can be applied as clinically indicated. Supportive care for thrombocytopenia or anemia, such as transfusions, may be managed according to institutional guidelines. The use of colony-stimulating growth factors should be considered. Febrile neutropenia or evidence of infection associated with neutropenia must be assessed immediately and treated appropriately and in a timely manner according to institutional guidelines.

Weight Loss

Anorexia and weight loss should be managed according to local standard of care including nutritional support. Pharmacologic therapy should be considered for appetite enhancement when not prohibited by a particular protocol.

Corrected QT Prolongation

The effect of orally administered Cabozantinib 140 mg qd on QTc interval was evaluated in a placebo-controlled study in subjects with medullary thyroid cancer (MTC). A mean increase in QTcF of 10-15 ms was observed after 4 weeks after initiating Cabozantinib treatment. A concentration-QTc relationship could not be definitively established. Changes in cardiac wave form morphology or new rhythms were not observed. No Cabozantinib-treated subjects in this study had a QTcF > 500 ms. Review of the larger safety database (approximately 5000 subjects exposed to Cabozantinib in clinical trials and in post-marketing experience) confirmed the absence of safety concerns associated with QT prolongation. There were no events of torsades de pointes reported.

Concomitant treatment with strong cytochrome P450 (CYP) 3A4 inhibitors, which may increase Cabozantinib plasma concentrations, should be avoided.

If at any time on study there is an increase in QTcF to an absolute value > 500ms, two additional ECGs must be performed with intervals not less than 3-min apart within 30min after initial ECG.

If the average QTcF from the three ECGs is > 500 ms, the following actions must be taken:

- Interrupt Cabozantinib treatment
- Immediately notify the Sponsor
- Hospitalize symptomatic subjects (e.g., with palpitations, dizziness, syncope, orthostatic hypotension, a significant ventricular arrhythmia on ECG) for a thorough cardiology evaluation and management
- Consider cardiology consultation for asymptomatic subjects for evaluation and management
- Check electrolytes, especially magnesium, potassium and calcium; correct abnormalities as clinically indicated
- Check concomitant medications for any medication that may have contributed to QT prolongation, and if possible, discontinue these medications (<http://www.qtdrugs.org>)
- Repeat ECG triplicates hourly until the average QTcF is \leq 500 msec, or otherwise determined by consultation with a cardiologist or appropriate expert.

Subjects with QTc prolongation and symptoms must be monitored closely until the QTc elevation and symptoms have resolved. Cabozantinib treatment may be restarted at a reduced dose level if all of the following conditions are met:

- Symptoms are determined to be unrelated to the QT interval prolongation
- The QTcF value > 500 ms is not confirmed
- Cabozantinib treatment has been interrupted through a minimum of 1 week following the return of the QTcF to \leq 500 ms.
- QT prolongation can be unequivocally associated with an event other than Cabozantinib administration and is treatable/has been resolved
- Sponsor has reviewed all available information and has agreed to the continuation of study treatment

Following reinitiation of study treatment, ECGs must be repeated weekly for 2 weeks, then every 2 weeks for 1 month, then according to the protocol-defined time points.

Cabozantinib treatment must be permanently discontinued if either of the following applies:

- Cardiac evaluation confirms that symptoms are the consequence of QT interval prolongation
- Recurrence of QTcF prolongation after reinitiation of study treatment at a reduced dose

Infections and Infestations

Infections are commonly observed in cancer subjects. Predisposing risk factor include a decreased immune status (e.g., after myelosuppressive anticancer therapies, splenectomy), destructive growth of the underlying malignancy including bone marrow infiltration with suppression of normal hematopoiesis, as well as the presence of IV devices.

Infections and abscesses should be treated with appropriate local care and systemic therapy. Cabozantinib should be interrupted until adequate healing has taken place.

Fatigue

Common causes of fatigue, such as anemia, deconditioning, emotional distress (depression and/or anxiety), poor nutrition, dehydration, sleep disturbance, and hypothyroidism should be ruled out and treated according to standard of care. Pharmacological management should be considered after disease specific morbidities have been excluded when not prohibited. Monitor TSH with Pembro.

Electrolyte Disorders

Serum electrolyte disorders including hyponatremia, hypokalemia, hypomagnesemia, and hypophosphatemia have been reported during treatment with Cabozantinib, and serum electrolyte levels should be monitored frequently while receiving Cabozantinib. Clinically relevant electrolyte disorders should be managed according to the dose modification guidelines as clinically indicated. Standard clinical practice guidelines should be used for management of electrolyte disorders and may include oral or IV replacement.

Endocrine Disorders

Treatment-emergent elevation of thyroid-stimulating hormone (TSH) has been observed with Cabozantinib treatment. Currently available data are insufficient to determine the mechanism of thyroid function test alterations and its clinical relevance. Management of thyroid dysfunction (e.g., symptomatic hypothyroidism) should follow accepted clinical practice guidelines.

Hepatocellular Toxicity

Elevations of aminotransferases (ALT and AST) and bilirubin have been observed during treatment with Cabozantinib. It is recommended that subjects with elevation of ALT, AST, and/or bilirubin have more frequent laboratory monitoring of these parameters. If possible, hepatotoxic concomitant medications should be discontinued in subjects who develop increased values of ALT, AST, or bilirubin, and other causes (e.g., cancer related, infection) should be evaluated.

Management guidelines for hepatotoxicity related to Cabozantinib treatment are in **Appendix E**. More frequent monitoring of transaminases should be considered and study treatment should be held until the etiology of the abnormalities is determined and these abnormalities are corrected or stabilize to clinically acceptable levels (e.g., baseline grade or lower). If hepatic toxicity resolved during a temporary hold and was deemed related to study treatment, then study treatment may be restarted at a reduced dose. Study treatment should be discontinued if hepatic dysfunction is not reversible despite temporary interruption of study treatment.

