4.3.3 Screening and Enrollment Guidelines

Prior to any study-required tests, subjects must first provide written informed consent to participate in this study.

Pre-treatment evaluation and their corresponding timeframes **to screen for and verify eligibility** for study enrollment include the following:

- Medical History: within 4 weeks
- Physical Exam, Vitals: within 2 weeks prior to treatment initiation
- ECG: within 4 weeks
- Imaging to confirm disease at baseline: scans must be within 8 weeks
- ECOG Performance Status: within 2 weeks
- CBC w/ diff, platelets: within 2 weeks
- CMP (Alk phos, total bilirubin, AST, ALT, and albumin): within 2 weeks
- Urine protein/creatinine ratio (UPCR): within 2 weeks
- Urine/serum pregnancy test: within 4 weeks
- TSH: at baseline
- Viral serologies (hepatitis, HIV): these will be checked to assess current or past infection and viral load as indicated

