11. STUDY CALENDAR

Baseline evaluations are to be conducted prior to start of protocol therapy as noted in the study calendar. In the event that the patient's condition is deteriorating, laboratory evaluations should be repeated within 48 hours prior to initiation of the next cycle of therapy.

	Pre-enrollment	Planned Cabo/Pembro Treatment *			Safety (100-days after final dose)	1-year Post Treatment Initiation	Off - Study
Assessment:	Screening	Cycle 1	Cycles 2 - 8	Cycles 9 - 17			
Visit Windows	Day -30 to -1	(± 3 days)	(± 3 days)	(± 7 days)	(+14 days)	(+14 days)	---
Informed consent	X						
Demographics, medical history	≤ 28 days						
Physical exam	≤ 14 days	X / Day 1 (C1-C8)		X / Day 1 of odd cycle	X	X	
Weight	≤ 28 days	X / Day 1 (C1-C8)			X	X	
Height	≤ 28 days	X					
ECOG PS	≤ 14 days	X / Day 1 (C1-C8)		X / Day 1 of odd cycle	X	X	
Vital signs	≤ 14 days		X / Day 1 of every cycle		X	X	
12-lead ECG	≤ 4 weeks	As clinically indicated.		As clinically indicated	As clinically indicated	As clinically indicated	
CBC w/ diff, platelets	≤ 14 days	Day 1 all cycles. Record in the eCRF: ANC, plts, Hemoglobin			X	X	
CMP	≤ 14 days	Day 1 of every cycle / only record results for the following in the eCRF: alk phos, total bilirubin, AST, ALT, albumin			X	X	
Hepatitis screening	X						
PT/INR, aPTT	≤ 14 days						
Urinalysis	≤ 14 days	X/ Day 1 of cycles 1 - 8		As clinically indicated	As clinically indicated	As clinically indicated	
Urine chemistry (UPCR)	≤ 14 days	X	Q6 weeks at clinic visit	As clinically indicated	As clinically indicated	As clinically indicated	
Pregnancy test	≤ 28 days	X					
TSH	≤ 14 days	X	Q6 weeks at clinic visit				
CA19-9	≤ 14 days	X, optional	CA19-9 may be evaluated at physician discretion per institutional standards.				

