				
 Participants with diarrhea/colitis should be advised to drink liberal quantities of clear fluids. If sufficient oral fluid intake is not feasible, fluid and electrolytes should be substituted via IV infusion
AST or ALT elevation or Increased Bilirubin	Grade 2 ^a	Withhold	
 Administer corticosteroids (initial dose of 0.5 - 1 mg/kg prednisone or equivalent) followed by taper 	
 Monitor with liver function tests (consider weekly or more frequently until liver enzyme value returned to baseline or is stable)
	Grade 3 ^b or 4 ^c	Permanently discontinue	
 Administer corticosteroids (initial dose of 1 - 2 mg/kg prednisone or equivalent) followed by taper 	
Type 1 diabetes mellitus (T1DM) or Hyperglycemia	New onset T1DM or Grade 3 or 4 hyperglycemia associated with evidence of β -cell failure	Withhold ^d	
 Initiate insulin replacement therapy for participants with T1DM Administer anti-hyperglycemic in participants with hyperglycemia 	
 Monitor participants for hyperglycemia or other signs and symptoms of diabetes
Hypophysitis	Grade 2	Withhold	
 Administer corticosteroids and initiate hormonal replacements as clinically indicated 	
 Monitor for signs and symptoms of hypophysitis (including hypopituitarism and adrenal insufficiency)
	Grade 3 or 4	Withhold or permanently discontinue ^d		
Hyperthyroidism	Grade 2	Continue	
 Treat with non-selective beta-blockers (eg, propranolol) or thionamides as appropriate 	
 Monitor for signs and symptoms of thyroid disorders
	Grade 3 or 4	Withhold or permanently discontinue ^d		
Hypothyroidism	Grade 2, 3, or 4	Continue	
 Initiate thyroid replacement hormones (eg, levothyroxine or liothyronine) per standard of care 	
 Monitor for signs and symptoms of thyroid disorders

Nephritis and renal dysfunction: grading according to increased creatinine or acute kidney injury	Grade 2	Withhold	
 Administer corticosteroids (prednisone 1 to 2 mg/kg or equivalent) followed by taper 	
 Monitor changes of renal function
	Grade 3 or 4	Permanently discontinue		

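### The study calendar does not carry out Section 7.2.2's electrolyte monitoring for magnesium and phosphate, and no electrolyte or creatinine value is stored, so these adverse events are not systematically ascertained

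*Combined protocol and SAP*

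**What the plan says.** **Expected events.** Section 7.2.2 lists laboratory adverse events seen in at least 5% of cabozantinib-treated subjects. The list includes the run "hypothyroidism, hypokalemia, hypomagnesemia, thrombocytopenia, hypocalcemia, hypophosphatemia" and, further on, hyponatremia. Under electrolyte disorders the same section adds "Serum electrolyte disorders including hyponatremia, hypokalemia, hypomagnesemia, and hypophosphatemia have been reported during treatment with Cabozantinib", and then says "serum electrolyte levels should be monitored frequently while receiving Cabozantinib". It gives no analyte list, no interval and no pointer to the calendar.

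**Scheduled tests.** The Section 11 calendar has a CMP row for Day 1 of every cycle, with results to be recorded only "for the following in the eCRF: alk phos, total bilirubin, AST, ALT, albumin". The CBC row reads "Day 1 all cycles. Record in the eCRF: ANC, plts, Hemoglobin". No row names magnesium, phosphate or an electrolyte panel. The screening list in Section 4.3.3 describes the panel by the same five analytes: "CMP (Alk phos, total bilirubin, AST, ALT, and albumin): within 2 weeks".

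**Event-triggered test.** If the average QTcF of three ECGs exceeds 500 ms, Section 7.2.2 says "Check electrolytes, especially magnesium, potassium and calcium; correct abnormalities as clinically indicated". This is the only explicit magnesium check. No phosphate test is specified anywhere.

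**Creatinine.** Section 3.1.5 uses it for eligibility, and Table 19 in Appendix F uses it for an immune-related toxicity: "Nephritis and renal dysfunction: grading according to increased creatinine or acute kidney injury". It is in neither the Section 4.3.3 parenthesis nor the eCRF results list.

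**AE route.** Under Section 10.1 a laboratory abnormality that the investigator considers clinically significant is an adverse event. It is recorded on the AE form with its CTCAE version 5 grade and each grade change. Section 9.5 then tabulates the maximum grade per category.

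**The concern.** A monitoring statement has effect only if something schedules the test and something keeps the result. Other cabozantinib laboratory risks discussed in Section 7.2.2 did reach the calendar: proteinuria as UPCR and thyroid effects as TSH, both every six weeks in cycles 2 to 8, and liver toxicity as stored AST, ALT and bilirubin. The electrolyte statement has no counterpart, which looks more like an omission than a decision.

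Secondary objective 1.2.1, the proportion of participants with adverse events, is at stake. Low magnesium or phosphate without symptoms is found only by a blood test; the open-ended questioning in Section 10.1 will not reveal it. If testing depends on who happens to be tested, the reported proportion reflects testing practice as well as toxicity. A low figure could then be read as good tolerability of this combination in pancreatic cancer. Grades matter too, because Section 7.2.3 ties withholding of cabozantinib to CTCAE grade and Section 9.5 reports by grade.

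**Working it through.** The plan states no figure for this point, so there is none to reproduce. The check is a comparison of sections followed by one line of arithmetic.

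**Step 1: each named disorder against the calendar and the eCRF.**

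| Disorder (7.2.2, at least 5%) | Test in a calendar row | Value sent to eCRF |
|---|---|---|
| Hypokalemia | Not named; possibly in the CMP | No |
| Hyponatremia | Not named; possibly in the CMP | No |
| Hypocalcemia | Not named; possibly in the CMP | No |
| Hypomagnesemia | None | No |
| Hypophosphatemia | None | No |

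The entries marked as possibly in the CMP are an assumption, because the documents do not give the panel's full content. None of the 5 disorders has a stored value, and 2 of the 5 have no identifiable scheduled test.

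**Step 2: stored laboratory values.** The CMP row sends 5 results to the eCRF and the CBC row sends 3, so 5 + 3 = 8 are explicitly directed there. None is an electrolyte or creatinine.

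**Step 3: what the CMP must contain.** Section 3.1.5 needs creatinine or creatinine clearance within 14 days of starting treatment. The CMP is the only calendar row that could supply serum creatinine. The five-analyte parenthesis in Section 4.3.3 therefore cannot be the whole panel, and the calendar's rule limits what is recorded, not what is measured.

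**Step 4: what the AE form recovers.** For an event to be counted, the analyte must be tested, the result must be abnormal, and the investigator must judge it clinically significant. For magnesium and phosphate the first condition is unscheduled. For sodium, potassium, calcium and creatinine it may be met each cycle, but the grade entered cannot be derived or checked from a stored value.

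**Step 5: size.** Inputs are 23 enrolled patients (Section 9.2) and the 5% floor (Section 7.2.2).

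- Expected patients with the event, per analyte: 23 × 0.05 = 1.15, about 1.2.
- Chance of at least one such patient, taking patients as independent: 1 − 0.95^23 = 1 − 0.307 = 0.69.
- If d is the probability that a patient with the abnormality is tested and recorded, the expected recorded count is 1.15 × d. The documents give no value for d, so the range is 0 to 1.15.

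**The case against.** The strongest reply is that the AE pathway already does the work. Clinically significant abnormal chemistry is an adverse event, it is entered with a CTCAE grade, and AE forms are trial data. Section 7.2.2 is itself operative text, and silence in the calendar does not cancel it. It also calls for electrolyte monitoring with vomiting and correction of abnormalities with diarrhea. Section 11 asks for repeat laboratory tests within 48 hours before the next cycle in a deteriorating patient, and the QTc procedure has its own magnesium, potassium and calcium check. Limited laboratory transcription is a reasonable choice in a small single-center trial. Monitoring and audit under Sections 13.2.1 and 13.2.2 can check entries, and eligibility creatinine is confirmed from laboratory copies under Section 4.4.

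Much of this stands, and it rules out several stronger readings that a reader might infer:

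- **That these events cannot be ascertained or graded at all.** The AE form captures those that are found.
- **That the eCRF holds only five laboratory results.** Five is the count for the CMP row; ANC, platelets and hemoglobin are stored as well.
- **That sodium, potassium, calcium and creatinine are not tested.** The documents restrict their recording, and creatinine must be tested under Section 3.1.5.
- **That reported rates will be near zero.** Nothing in the documents fixes how often sites will test.

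The reply does not supply a schedule for magnesium or phosphate. The other prompts follow symptoms, deterioration or a QTc finding, so a patient without symptoms may never be tested. Source verification of a sample of charts is also not the same as deriving grades from stored values for everyone.

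**Conclusion.** The point holds as a cheap improvement. Section 7.2.2 and the Section 11 calendar do not agree on electrolyte monitoring. For magnesium and phosphate, ascertainment rests on unscheduled testing, and the incidence reported under objective 1.2.1 is probably too low. For all five electrolytes and for creatinine, CTCAE grades cannot be derived or verified from stored values.

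The size is modest: about 1.2 expected patients of 23 per analyte at the 5% floor, some of whom would be found anyway. This rests on two assumptions. The first is that the floor, which comes from cabozantinib monotherapy, carries over to this combination and population. The second is that all 23 enrolled patients are treated. The documents give no upper rate, so none is used. PFS, the interim rule and the final decision threshold are untouched.

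**What to change.** 1. Reconcile Sections 4.3.3, 7.2.2 and 11 so that the monitoring statement and the calendar agree. Which electrolytes are meant, and when they are tested, is for the sponsor to decide. Alternatively, revise the statement in Section 7.2.2 and say in Section 9.5 that these adverse events are not systematically ascertained, so that a low rate is not read as evidence of tolerability.
2. State what the CMP contains, so that the parenthesis in Section 4.3.3 is not taken for the full panel.
3. Add the electrolyte and creatinine results that are measured to the eCRF results list, so that grades can be derived and checked against AE entries.

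The cost is a few more eCRF fields with their data entry and, depending on the sponsor's decision, extra analytes on a blood draw that is already scheduled each cycle.
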